9.8.2 Pregnancy testing

Pregnancy testing will consist of serum testing at the SFU Visit and urine testing at all other visits.

The Baseline Visit urine pregnancy test result must be negative prior to enrollment of the subject. A negative urine pregnancy test result should be obtained immediately prior to each administration of study drug and at all subsequent visits. Pregnancy tests should be administered to all female subjects of childbearing potential, regardless of their use of birth control.

9.8.3 Vital signs

Vital signs will be collected at every visit and will include systolic and diastolic blood pressure, pulse rate, and body temperature (oral, axillary, or otic). Subjects should be sitting for 5 minutes before and during vital signs assessments.

Vital signs are to be measured prior to blood sampling, and prior to dosing, where applicable.

Body weight will be measured at the time points specified in the schedule of study assessments (Table 5–1).

9.8.4 12-lead ECGs

Twelve-lead standard ECGs will be recorded at the visits specified in Table 5–1, and read by a central ECG laboratory.

Full details of ECG recording will be provided in the ECG Manual.

9.8.5 Physical examination

The physical examination will include general appearance; ear, nose, and throat; eyes, hair, and skin; respiratory; cardiovascular; GI; musculoskeletal; hepatic; neurological (including limb reflexes); and mental status. Physical examination will be performed at the at the time points specified in the schedule of study assessments (Table 5–1). Findings considered clinically significant changes since the physical examination at the Screening Visit of PS0010 will be recorded as AEs.

9.8.6 Assessment of suicidal ideation and behavior

Suicidal ideation and behavior will be assessed by trained study personnel using the eC-SSRS. This scale will be used to assess suicidal ideation and behavior that may occur during the study. The visits at which the eC-SSRS assessments will be performed are specified in the schedule of study assessments (Table 5–1).

The eC-SSRS is a standardized and validated instrument developed for the assessment of the severity and frequency of suicidal ideation and behavior (Mundt et al, 2010; Posner et al, 2011). Subjects respond to standardized clinical questions that are presented in a uniform fashion. The eC-SSRS defines five subtypes of suicidal ideation and behavior in addition to self-injurious behavior with no suicidal intent. The eC-SSRS takes approximately 3 to 10 minutes to complete.

Refer to Section 6.3 for eCSSRS-related withdrawal criteria.

9.8.7 Data Monitoring Committee

The DMC membership includes clinicians knowledgeable about the disease or the treatment. The DMC will include a statistician, and at a minimum, specialists in dermatology and infectious

disease. All members have experience and expertise in clinical trials. Board members may not participate in the study as principal or co-Investigators, or as study subject care physicians. The duration of membership for the DMC will be inclusive of planned analyses for PS0011. The DMC may also be asked to provide a review of final study results, as deemed appropriate.

The detailed role, scope, responsibilities, and complete procedures, as well as the identity of the DMC members, will be described in a separate charter document.

The DMC procedures will ensure that data remain blind to the study team and Investigators at all times throughout the conduct of the study.

A Cardiovascular Adjudication Committee will also periodically review the safety data from this study. Details will be described in a separate charter document.

10 ASSESSMENT OF PHARMACOKINETIC VARIABLES

Blood samples for measurement of PK ([Section 4.2](#)) will be collected at the time points specified in the schedule of study assessments ([Table 5-1](#)).

At dosing visits, blood samples will be drawn prior to dosing, and will be drawn at the same time of the sampling for clinical laboratory tests. The time and date of collection will be recorded in the eCRF.

Instructions pertaining to sample collection, processing, storage, labeling, and shipping are provided in the laboratory manual for this study. Detailed information on sample analysis will be provided in a bioanalytical report.

11 ASSESSMENT OF IMMUNOLOGICAL VARIABLES

Blood samples for measurement of antibodies to bimekizumab will be collected at the visits specified in [Table 5-1](#). The threshold for antibody positivity will be defined prior to analysis.

At dosing visits, blood samples will be drawn prior to dosing, and will be drawn at the same time of the sampling for clinical laboratory tests. The time and date of collection will be recorded in the eCRF.

Instructions pertaining to sample collection, processing, storage, labeling, and shipping are provided in the laboratory manual for this study. The presence of antibodies to bimekizumab will be determined using a validated bioanalytical method. Detailed information on sample analysis will be provided in a bioanalytical report.

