4.3 Immunological variable

The immunological variable is anti-bimekizumab antibody levels prior to and following study treatment.

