14.5 Planned immunological analyses

Immunological variables will be analyzed for all subjects in the PK-PPS.

Anti-bimekizumab antibody data will be summarized by PS0010/PS0011 treatment group at each scheduled visit. The summary of anti-bimekizumab antibody levels will follow a similar approach to that used for the summary of bimekizumab plasma concentrations. Additional analyses related to antibody positivity will be performed and will be described in greater detail in the SAP.

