4.7 Examination of subgroups

Subgroup analyses will be performed on the secondary efficacy variables.

The following subgroup analyses will be performed:

- Age (<65 years, ≥65 years)
- Gender (male, female)
- Duration of disease at PS0010 Baseline (<median, ≥median)
- Region (North America [Canada, USA], Europe and Asia [Czech Republic, Hungary, Poland, Japan])
- Body weight at PS0010 Baseline (<100 kg, ≥100 kg)
- Body Mass Index (BMI) at PS0010 Baseline (<25 kg/m², 25 to <30 kg/m², ≥30 kg/m²)
- Prior biologic systemic therapy at PS0010 Baseline (yes, no)

- Prior anti-TNF therapy at PS0010 Baseline (yes, no)
- Any prior systemic therapy at PS0010 Baseline (yes, no)
- Anti-bimekizumab antibody positivity at any time on treatment during PS0010 or PS0011 (yes, no)
- PASI score at PS0010 baseline (<20, ≥20)
- Psoriasis BSA at PS0010 baseline (<20%, ≥20%).

These summaries, using the FAS, will be based on imputed data (NRI) and will include descriptive statistics only. If there are less than 2 subjects in any subgroup category/treatment group, then that subgroup category will not be summarized. If it is possible to collapse subgroups with more than 2 categories, then collapsing may be done to get categories with no less than 2 subjects per subgroup category/treatment group.

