8.2 Other safety analysis

8.2.1 TEAEs

The following summaries will be provided by PS0011 treatment group and for the “All bimekizumab” group. In addition, all summaries of TEAEs “per 100 subject years” will display EAIR and EAER:

- Incidence of TEAEs – Overview
- Incidence of TEAEs per 100 subject years by SOC, HLT and PT
- Incidence of TEAEs per 100 subject years by SOC, HLT, PT and by Timing of Onset Relative to Anti-bimekizumab Antibody Status
- Incidence of TEAEs by Decreasing Frequency of PT
- Incidence of TEAEs by Maximum Severity, SOC, HLT and PT
- Incidence of Non-Serious TEAEs by SOC, HLT and PT
- Incidence of Non-Serious TEAEs Above Reporting Threshold of 5% by SOC and PT

The incidence of TEAEs per 100 subject years will also be summarized for PS0010 and PS0011 combined, where treatment emergence and exposure at risk are relative to the first dose of study drug in PS0010. In the case of a subject that switches study treatment when starting PS0011, exposure at risk to PS0010 treatment will end the day prior to the first PS0011 dose. Adverse events that occur on the PS0011 baseline visit date will be attributed to the PS0010 treatment.

The only exception to this definition is for the following types of events:

- Those that code to a High Level Term (HLT) of “Injection Site Reactions”
- Those which have been designated as an Injection Reaction on the AE CRF and do not code to a System Organ Class (SOC) of “Investigations”
- Those which have been identified as a hypersensitivity reaction or an anaphylactic reaction

When any of these events occur on the date of treatment switch at PS0011 Baseline, the AE will be attributed to the treatment initiated in PS0011.

All AE summaries will be ordered alphabetically by SOC and HLT within SOC and in terms of decreasing frequency for PT within HLT in the “All bimekizumab” treatment group.

For each subject and each AE, the worst severity recorded will be attributed and used in the by-severity summaries. Similarly, the worst causality (most related to treatment) will be attributed and used in the by-causality summaries. If severity or causality is missing, the worst case will be assumed.

If the intensity of an AE is unknown, it will be considered as severe. If the relationship to study drug is missing, it will be considered as related.

Additional tables will summarize TEAEs by relationship to study medication, TEAEs leading to withdrawal from the study, treatment-emergent SAEs, and deaths:

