9.2 Immunogenicity

9.2.1 Anti-bimekizumab antibodies

Subjects with a positive on-treatment (i.e., excluding PS0010 Baseline) anti-BKZ antibody result in either PS0010 or PS0011 will be classified as anti-BKZ positive.

Anti-BKZ antibody status will be summarized for each PS0010/PS0011 treatment group at each scheduled PS0010 and PS0011 visit using the PK-PPS analysis set. The first occurrence of anti-BKZ antibody positivity will also be presented for each PS0010/PS0011 treatment group at each scheduled PS0010 and PS0011 visit.

The anti-BKZ antibody status will be determined for each visit where samples are taken for drug concentration means. The cut point for determining whether the anti-bimekizumab antibody level is sufficiently high to be considered anti-BKZ antibody positive is not yet known. However, this will be determined prior to the database lock of the PK and anti-BKZ antibody data.

A line plot of the percentage of anti-BKZ antibody positive subjects at each visit will be produced by PS0010/PS0011 treatment group. All individual subject-level anti-BKZ antibody results will be listed.

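### The SAP's anti-bimekizumab positive class ignores the subject's own pre-bimekizumab result, so unchanged pre-existing reactivity counts the same as antibody that appeared on drug

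*Protocol*

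**What the plan says.** Protocol 4.3 defines the variable with a before and an after: "The immunological variable is anti-bimekizumab antibody levels prior to and following study treatment". Protocol section 11 says of the threshold: "The threshold for antibody positivity will be defined prior to analysis". Protocol 14.5 hands the rest to the SAP: "Additional analyses related to antibody positivity will be performed and will be described in greater detail in the SAP".

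SAP 9.2.1 then gives the subject-level rule: "Subjects with a positive on-treatment (i.e., excluding PS0010 Baseline) anti-BKZ antibody result in either PS0010 or PS0011 will be classified as anti-BKZ positive". On the threshold it says: "The cut point for determining whether the anti-bimekizumab antibody level is sufficiently high to be considered anti-BKZ antibody positive is not yet known". It adds that "this will be determined prior to the database lock of the PK and anti-BKZ antibody data".

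Antibody status is used in two other places:

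- SAP 4.7 lists it as a subgroup factor for the secondary efficacy variables, PASI90 and IGA response: "Anti-bimekizumab antibody positivity at any time on treatment during PS0010 or PS0011 (yes, no").
- SAP 8.2.1 plans a safety table: "Incidence of TEAEs per 100 subject years by SOC, HLT, PT and by Timing of Onset Relative to Anti-bimekizumab Antibody Status".

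**The concern.** The rule removes PS0010 Baseline from the samples that can make a subject positive, but does not use it as a comparator. Nothing requires a negative result before drug or a rise over it, and no category is set aside for pre-existing reactivity. A subject above the cut point before the first dose and at the same level afterwards is positive under this rule.

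The term on-treatment is also not limited to bimekizumab. Only PS0010 Baseline is excluded, so any later PS0010 sample from a placebo subject can qualify.

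Assessing immunogenicity is one of the study's other objectives. A class that mixes antibody present before drug with antibody that appeared on drug does not answer that question cleanly, and the mixture passes into any table built on the class.

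**Working it through.** The plan states no figure here to reproduce: no cut-point value, no rate of pre-drug reactivity and no expected rate of positivity. The check is to apply the rule as written.

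**Inputs**

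- Qualifying samples: every PS0010 or PS0011 result except PS0010 Baseline (SAP 9.2.1).
- Criterion: the antibody level is above one cut point (SAP 9.2.1).
- Sampling: protocol Table 5-1 has an antibody sample at PS0011 Baseline, taken at the PS0010 Week 12 visit. Its footnotes require blood to be drawn before dosing. For a PS0010 placebo subject that sample precedes any bimekizumab.
- Treatment paths: placebo subjects either stay on placebo or move to bimekizumab 160mg (protocol 7.2).

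**Rule applied to subject histories**

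| Subject's history | Class under SAP 9.2.1 | Class if compared with the last pre-bimekizumab sample |
|---|---|---|
| Bimekizumab in PS0010; negative at PS0010 Baseline, positive later | Positive | Treatment-emergent |
| Bimekizumab in PS0010; positive at PS0010 Baseline, same level later | Positive | Pre-existing |
| Bimekizumab in PS0010; positive at PS0010 Baseline, prespecified rise later | Positive | Treatment-emergent |
| Placebo to bimekizumab 160mg; negative at PS0010 Baseline, positive at PS0011 Baseline before dosing, no rise later | Positive | Pre-existing |
| Placebo to Placebo; any positive after PS0010 Baseline | Positive | Unexposed, shown separately |

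Five different histories receive one label. In the fourth, a single sample taken before any bimekizumab is enough.

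**Size, in symbols**

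Let *b* be the share of subjects already reactive before bimekizumab who stay positive without a rise. Let *t* be the rate of new positivity among the rest.

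- SAP rule: *b* + (1 − *b*)*t*
- Rule with a pre-drug reference: (1 − *b*)*t*
- Difference: *b*

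The overcount equals *b*. The documents give neither *b* nor *t*.

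**Does another section correct this?**

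- SAP 9.2.1 also tabulates status and first occurrence of positivity at each scheduled PS0010 and PS0011 visit, and lists individual results. These are group-level displays or listings and leave the derived class unchanged.
- Protocol 14.5 would summarise antibody levels much as plasma concentrations, which under protocol 14.4 includes change from PS0010 Baseline. SAP 9.2.1 does not repeat that level summary, although SAP 3.11 reports no changes to the protocol's analyses. Even if produced, it would reclassify nobody.
- SAP 4.7 repeats the on-treatment wording for its subgroup, so the class carries over directly.
- SAP 8.2.1 gives no derivation for its table. Whether it uses this class, and how it would place a subject reactive from the start, is unknown.

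**The case against.** The strongest reply is that pre-drug reactivity is not hidden. If PS0010 Baseline is among the scheduled visits, the first-occurrence table separates subjects first positive before drug from those first positive later, and the listings show every result. This stands as a mitigation for the headline rates, and it would be wrong to say that the plan ignores pre-drug results altogether. It does not reach the yes/no class.

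A second reply is that the SAP 4.7 factor is labelled as positivity on treatment and does not claim to show drug-induced antibody. That is fair. A reader might infer that mixing the two kinds of positive dilutes a real effect of antibody on response. The documents do not show that antibody present before drug matters less than antibody formed on drug, so dilution cannot be asserted. The label still does not fit a placebo subject whose only positive sample precedes bimekizumab.

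Third, the setting is modest. Immunogenicity sits among the other objectives, no inferential analysis is planned (protocol 14.2), and the subgroup is one of twelve descriptive ones. All of that stands and limits the weight of the point.

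A reader might also infer that the open cut point could be chosen with knowledge of treatment, because selected Sponsor staff are unblinded when PS0010 is. The documents do not support this. Protocol section 11 requires a validated method, SAP 9.2.1 fixes the cut point before the PK and antibody data are locked, and nothing gives the choice to unblinded staff. Nor does anything suggest different cut points for the two studies.

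**Conclusion.** The point holds as a defect in one stated rule. Followed exactly, SAP 9.2.1 puts unchanged pre-existing reactivity, and reactivity on PS0010 placebo before any bimekizumab, in the same class as antibody that appeared on drug. The class enters the SAP 4.7 subgroup, and may enter the SAP 8.2.1 table.

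The overcount equals the share of subjects with such reactivity. A reader might infer that immunogenicity is heavily overstated, but without a pre-drug rate the documents support no figure, large or small. If no subject is reactive before drug, the rule does no harm.

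The conclusion assumes that the cut point will be a cut on the level, as SAP 9.2.1 words it, and not a change relative to baseline. No test or error rate is affected. The change is worth making because the rule is explicit and the correction is cheap.

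**What to change.** In SAP 9.2.1:

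- Take as reference the last sample before the first bimekizumab dose. This is PS0010 Baseline for subjects randomised to bimekizumab and PS0011 Baseline for subjects moving from placebo to bimekizumab. PS0010 Baseline alone would not serve for the latter, because it misses reactivity that appeared on placebo.
- Classify as treatment-emergent those negative at reference and positive after a bimekizumab dose, and those positive at reference with a rise in antibody level prespecified from the assay validation.
- Show subjects positive at reference without that rise as pre-existing.
- Show subjects with a missing reference separately, rather than counting them as negative.
- Report Placebo to Placebo subjects separately as unexposed.

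Use the treatment-emergent class in SAP 4.7 and 8.2.1, state in 8.2.1 how timing relative to antibody status is derived, and keep the any-positive class as supportive.

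The cost is SAP wording and derivation, with no new samples: PS0011 Baseline is in protocol Table 5-1, and SAP 9.2.1 already refers to the PS0010 Baseline result. The rise has to be set from the assay validation, which the documents do not describe, and a few reference-positive subjects will depend on it. The positive subgroup also becomes smaller, so the SAP 4.7 limit of 2 subjects per category and treatment group may remove more cells.

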12 ASSESSMENT OF EFFICACY

12.1 Psoriasis Area and Severity Index

The PASI is the most commonly used and validated assessment for grading the severity of psoriasis in clinical studies (Feldman, 2004). The PASI quantifies the severity and extent of the disease and weighs these with the percentage of BSA involvement.

The degree of involvement is estimated across 4 body areas; head, upper limbs, trunk, and lower limbs and then transferred into a grade ([Table 12-1](#)).

The Investigator assesses the average redness, thickness, and scaliness of lesions in each body area (each on a 5-point scale); 0=none, 1=slight, 2=moderate, 3=marked, and 4=very marked.

The PASI score ranges from 0 to 72 with a higher score indicating increased disease severity.

Table 12–1: Body areas for calculation of percent BSA for PASI

Body area	Details of area	BSA	Degree of involvement of body area ^a
Head	Face, back of head	10%	0 to 6
Upper limbs	Left, right, upper lower, flexor surface, extensor surface	20%	0 to 6
Trunk	Front, back, groin	30%	0 to 6
Lower limbs	Left, right, upper lower, flexor surface, extensor surface, including buttocks	40%	0 to 6
Total		100%	

BSA=body surface area; PASI=Psoriasis Area and Severity Index

^a Where 0=none; 1=1% to <10% affected, 2=10% to <30% affected, 3=30% to <50% affected, 4=50% to <70% affected, 5=70% to <90% affected, 6=90% to 100% affected.

The PASI50, PASI75, PASI90, and PASI100 responses are based on at least 50%, 75%, 90%, and 100% improvement in the PASI score. The improvement will be based on changes from the PASI score at the Baseline of PS0010.

The PASI will be completed at the visits specified in [Table 5–1](#).

12.2 Investigator’s Global Assessment

A static IGA for psoriasis will be used to assess disease severity in all subjects during the study. The IGA will be completed at the visits specified in [Table 5–1](#).

The Investigator will assess the overall severity of psoriasis using the following 5-point scale:

5 point Investigator’s Global Assessment		
Score	Short Descriptor	Detailed Descriptor
0	Clear	No signs of psoriasis; post-inflammatory hyperpigmentation may be present
1	Almost clear	No thickening; normal to pink coloration; no to minimal focal scaling
2	Mild	Just detectable to mild thickening; pink to light red coloration; predominately fine scaling
3	Moderate	Clearly distinguishable to moderate thickening; dull to bright red, clearly distinguishable to moderate thickening; moderate scaling
4	Severe	Severe thickening with hard edges; bright to deep dark red coloration; severe/coarse scaling covering almost all or all lesions

12.3 Dermatology Life Quality Index

The DLQI is a questionnaire designed for use in adult subjects with psoriasis. The DLQI is a skin disease-specific questionnaire aimed at the evaluation of how symptoms and treatment affect patients' health related quality of life (QOL). This instrument asks subjects about symptoms and feelings, daily activities, leisure, work and school, personal relationships and treatment. It has been shown to be valid and reproducible in psoriasis patients. The DLQI score ranges from 0 to 30 with higher scores indicating lower health related QOL. A 5-point change in the DLQI score (DLQI response) has been reported to be meaningful for the patient (within-patient minimal important difference); while a DLQI absolute score of 0 or 1 indicates no or small impact of the disease on health related QOL. Subjects will be asked to complete the DLQI as outlined in the Schedule of Study Assessments ([Table 5-1](#)). Study site personnel should ensure that each subject completes the instrument prior to leaving the study site.

12.4 BSA affected by psoriasis

The BSA palm method will be used for the evaluation of BSA as follows:

Body surface area estimation uses the palm (subject's flat hand and thumb together, fingers included) as representing around 1% of the total BSA.

- Subject's palm=1%
- Head and neck=10% (10 palms)
- Upper extremities=20% (20 palms)
- Trunk=30% (30 palms)
- Lower extremities=40% (40 palms)
- Total BSA=100%

Evaluation of BSA will be completed at the visits specified in [Table 5-1](#).

12.5 Modified Nail Psoriasis Severity Index

Psoriatic nail disease will be evaluated at the Baseline Visit of PS0010 using the mNAPSI. All affected nails will be scored (0 to 3) for onycholysis/oil drop dyschromia, nail plate crumbling, and pitting and will be scored (0 for "no" or 1 for "yes") for leukonychia, nail bed hyperkeratosis, splinter haemorrhages and red spots in the lunula. The score for an individual nail ranges from 0 to 13 with higher scores indicative of more severe nail disease. The total mNAPSI score is the sum of the scores for each individual nail. If a nail is unaffected, it will be recorded as such and will not contribute to the total mNAPSI score. Subjects with nail disease at Baseline are defined as those with an mNAPSI score >0 at Baseline of PS0010.

The mNAPSI will be assessed at the visits specified in [Table 5-1](#).

